at the beginning of tenth grade. We describe below the specific operationalization of these three outcome measures (see Table 1 in Appendix for additional detail).

Sexual initiation

Sexual initiation is constructed as a dichotomous variable – participants are either coded as having ever had sex or not having ever had sex. Data used to assess the impact of the treatment (*PGC*) on sexual initiation are obtained from the following item on the *Participant Questionnaire*, which is administered to both treatment and control groups at baseline and the beginning of tenth grade:

- *Have you ever had any type of sex (oral, vaginal, or anal)?*

Persons who select *Yes* to the question are coded as 1, indicating that they have had sex. Persons who select *No* to the question are considered to not have ever had sex and are coded as 0 .

PGC will be considered to have a positive impact on sexual initiation if, as compared to participants who are assigned to the control group, a smaller proportion of participants who are offered *PGC* report sexual initiation at the beginning of tenth grade and the difference between groups is statically significant.

Times having sex

Times having sex is constructed as a continuous variable – the number of times in the past three months a participant engages in any type of sex (vaginal, oral, or anal).⁵ Data used to assess the impact of the treatment (*PGC*) on frequency of sex are obtained from the following item on the *Participant Questionnaire*, which is administered to both the treatment and control groups at baseline and the beginning of tenth grade:

- *In the past three months, how many times have you had any type of sex?*

Persons who indicate that they have never had any particular type of sex (vaginal, oral, or anal) or have not had any type of sex in the past three months are coded as having sex zero times.⁶

PGC will be considered to have a positive impact on times having sex if, at the beginning of the tenth grade, participants assigned to *PGC* report having sex fewer times than participants assigned to the control condition and the difference between groups is statically significant.

Number of sexual partners

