- ii. **Identify and flag invalid responses:** The second step in the data screening process is to inspect the data for instances in which responses are invalid because they are outside of a pre-determined range of plausible or acceptable values. Each questionnaire type (e.g., baseline, post-program) has a codebook, which is prepared by a PRG staff, that contains variable names, valid variable values or ranges of values, and when applicable value labels.¹² Referring to the codebook, a senior or lead research analyst performs diagnostics in Stata to ensure that responses to all analytic measures are valid (i.e., data are within ranges specified in the codebook). A data analyst inspects the data using two commands in Stata. First the analyst uses the command *sum variable_name*, which provides summary statistics (mean, minimum, maximum, standard deviation) for all numeric variables. The analyst checks that the minimum and maximum values are valid. If this command reveals there are values out of range, the analyst then inspects the data using the command, *tab variable_name, missing*, which provides a frequency table of all values (including missing values) so the analyst can identify and flag all values that are out of range as invalid and recode these values to missing (code as “.i”).

Data that are recoded to missing are treated according to our missing data approach. Briefly, our benchmark approach is to adjust missing baseline data and include in analysis; we exclude observations with missing outcome data from analysis.

- iii. **Identify and flag outliers:** The third step is to identify and flag severe outliers. Outliers (operationally defined below) are values that are extreme compared to other observations but are not plainly invalid. In the data cleaning process, we inspect outliers so that we can try to ascertain whether they are in fact true (or plausible) values or potentially a result of measurement error. The only variables for which we inspect outliers are those used in the construction of our outcome variables (times having vaginal sex, times having oral sex, times having anal sex, and number of sexual partners) because they have no upper limit (all other variables used in analysis are either categorical or have predicated upper and lower bounds). Our approach to identifying and flagging outliers is as follows.¹³

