- First, in Stata we use the *lv* (letter-value display) command to identify severe outliers. We define values as severe outliers according their relation to the interquartile range (IQR). Severe outliers are defined as values outside of the *outer fences* of the population distribution.
 - $IQR = Q_3(3^{rd} \text{ quartile or } 75^{th} \text{ percentile}) - Q_1(1^{st} \text{ quartile or } 25^{th} \text{ percentile})$

¹¹ See [Comparing and Evaluating Youth Substance Use Estimates from the NSDUH and Other Surveys](https://www.samhsa.gov/data/sites/default/files/NSDUH-M9-Youth-2012/NSDUH-M9-Youth-2012.pdf) retrieved December 7, 2018 from <https://www.samhsa.gov/data/sites/default/files/NSDUH-M9-Youth-2012/NSDUH-M9-Youth-2012.pdf>.

¹² Regardless as to whether data are nominal, ordinal, or continuous, all response options are coded in Stata as numeric values; values are labeled according to corresponding category names when data are nominal or ordinal. As an example, the variable gender is a nominal variable; however, it is treated as a dummy variable where females are coded as “1” and males are coded as “0”. The only acceptable values for this variable then are 0 and 1; any other values are out of range.

¹³ Rules for identifying outliers are informed by the following: Hamilton, Lawrence C. 2006. *Statistics with Stata: Updated for Version 9* and *NIST/SEMATECH e-Handbook of Statistical Methods*, <http://www.itl.nist.gov/div898/handbook/>.

- Upper outer fence: $Q3 + 3*IQ$
- Lower outer fence: $Q1 - 3*IQ$
- Second, we create an outlier indicator variable, where observations deemed severe outliers are coded as 1, all others are coded as 0.

Our benchmark analytic approach is to include data flagged as outliers in analysis, because we do not know for certain whether the values are true or invalid. However, we also run sensitivity analyses that exclude these data and report substantive differences in the results section of the report.

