$Crossover_{student\ T}$ - the proportion of students randomly assigned to the treatment group across all study schools who did not receive any PGC

$Base_{student\ T}$ - the number of students randomly assigned to the treatment group across all study schools

$Not\ Received_{student\ T}$ - the number of students randomly assigned to the treatment group across all study schools who did not receive any PGC

Contamination will be defined as study participants assigned to the control condition who received any amount of PGC programming during the course of the program implementation period.²⁸ This will be determined from attendance records within the *Attendance Tracking Database*. We will calculate contamination using the following formula:

$$Contamination_{student\ C} = \left(\frac{Received_{student\ C}}{Base_{student\ C}} \right)$$

where:

$Contamination_{student\ C}$ - the proportion of students randomly assigned to the control group across all study schools who received any amount of PGC

$Base_{student\ C}$ - the number of students randomly assigned to the control group across all study schools

$Received_{student\ C}$ - the number of students randomly assigned to the control group across all study schools who received any amount of PGC

Levels of crossover and contamination will be reported in the findings section of our final impact report.

- f. **Analytic approach for primary research questions:** As detailed in our primary research questions, this study investigates whether offering PGC to participants impacts their reported sexual initiation, number of times having sex, and number of sexual partners. We do this within the intent to treat (ITT) framework, which does not measure the effect of the participant's exposure to the treatment itself but rather the effect of the offer of the treatment relative to the offer of receiving the control condition. This framework maintains the integrity of the experimental structure by including all participants who were randomized (except those who attrite) in the analytic sample, thereby maintaining an exogenous assignment of participants to experimental condition. Bias can be insinuated, however, through self-selection if any participant who is randomized fails to provide outcome data.

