As outlined in the *Baseline equivalency* section, we will also produce diagnostic estimates of baseline equivalency on the pre-intervention outcome variables according to our benchmark approach and the sensitivity study alongside each other in an appendix of the report.
 3. **With unreliable data.** As discussed in the *Data cleaning* section, data for cases that are deemed unreliable are treated as *unit missing* and excluded from benchmark analyses. To test this, we will conduct sensitivity analyses that involve running identical empirical models with the unreliable data included. Analytic findings for both approaches will be presented alongside each other in an appendix of the impact report.

4. **Without outliers.** As discussed in the *Data cleaning* section, extreme data values are investigated and flagged as outliers. Our benchmark analytic approach is to include data flagged as outliers (i.e., extreme values that are not considered invalid) in analysis. We will also conduct sensitivity analyses that exclude these data and report substantive differences in the results section of the report.
5. **Condensed data collection windows.** Our benchmark approach is to include follow-up data from all participants who completed a questionnaire during their open data collection window, regardless of the time point in that window when it was completed. Data collection windows are broad to minimize attrition from the analytic sample. To examine whether or not this influences our results – and, in particular, whether or not study participants who respond later report different outcomes from those who respond earlier – we will conduct an analysis that examines the difference, if any, in response time between treatment and control participants and compares impact estimates for analytic samples without late responders. Late responders will be defined as those participants who complete their 10th grade questionnaire more than one month after the initiation of the 10th grade data collection window.

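### Sensitivity analysis 4 drops students on their own follow-up count, so it can shrink a real reduction in sexual frequency or partners; a run capped at a stated value should stand beside it

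*Combined protocol and SAP*

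**What the plan says.** Section 4c.iii (outliers) screens only the items behind two of the three primary outcomes: "times having vaginal sex, times having oral sex, times having anal sex, and number of sexual partners". A severe outlier lies beyond an outer fence; the upper one is the third quartile plus three interquartile ranges. The section does not say whether the fence is computed over all students or only those who answered the item, with arms pooled or separate, or on each item or the summed outcome.

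The benchmark keeps flagged values "because we do not know for certain whether the values are true or invalid". Section 4f.iv, item 4, adds: "We will also conduct sensitivity analyses that exclude these data", with any substantive difference to be reported among the results. Table 3 repeats the exclusion. A substantive difference is not defined.

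Three other provisions bear on this:
- Section 4c.v, step 4, deletes cases without 10th-grade outcome data.
- Section 4a codes inactive students as zero. For times having sex, those with no sex "in the past three months are coded as having sex zero times"; number of partners is handled in the same way.
- Section 4f describes the main analysis as "including all participants who were randomized (except those who attrite) in the analytic sample".

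**The concern.** The run is there to show whether a few doubtful values drive the result. A flag depends on the size of the student's 10th-grade answer, which the programme is meant to change. The benefit sought is fewer times and fewer partners, so under a true benefit the control arm has more students above any common fence and loses more of them. The estimate moves towards zero even if every answer is honest.

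The run therefore cannot separate two explanations of a smaller estimate: false reports inflated the benchmark, or real differences in the upper tail were deleted. No other planned analysis limits extreme values. Item 6 of 4f.iv changes the model form but keeps them. A true reduction in either count outcome could be reported as fragile when it is not.

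**Working it through.** The documents give no effect size, standard deviation, rate of recent sex or expected number of outliers, so there is no plan figure to reproduce. The check applies the fence rule to simulated counts.

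**1. Fence among non-zero reports**

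Assumptions:
- 680 analysed per arm. The Evaluation Abstract expects about 1,600 students; an assumed 15% loss gives 1,600 × 0.85 / 2 = 680.
- 20% of controls active in the past three months.
- Count among the active = 1 + negative binomial, with shape 0.3 (heavy tail), 0.5 or 1.0 (light tail).
- Fence = Q3 + 3 × IQR, arms pooled; 4,000 trials per scenario.
- Unadjusted difference in means on the total count.

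| Scenario | True difference | Exclusion keeps | Capping at the fence keeps |
|---|---|---|---|
| Mean among active falls from 9 to 7 | 0.20 × (7 − 9) = −0.40 | 22–76% | 63–94% |
| That, and share active falls from 20% to 17% | 0.17 × 7 − 0.20 × 9 = −0.61 | 63% | 88% |
| Only the share active falls | (0.17 − 0.20) × 9 = −0.27 | 84% | 96% |

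The ranges in the first row run from heavy to light tail; repeat runs moved their ends by at most about two points. At shape 0.5 exclusion kept about 49% and capping 83%, and exclusion removed about 4.8 controls against 2.2 PGC students per trial. So in the first scenario exclusion loses 24–78% of the true difference and capping loses 6–37%.

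With no true effect, neither method is biased. With no true effect and three false control values between 200 and 999, the benchmark shows −2.60, exclusion +0.02 and capping −0.16. Capping removes 1 − 0.16/2.60 = 94% of the artefact.

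**2. Fence over all students, zeros included**

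If at least 75% report 0, then Q1 = Q3 = 0, IQR = 0 and the upper fence is 0 + 3 × 0 = 0. Every active student is flagged. Exclusion leaves only zeros and capping turns every value into zero, so both give a difference of exactly 0.

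A second simulation used 800 per arm, mean 8 among active controls, negative binomial shape 0.7, PGC multiplying that mean by 0.7, no false values and 600 trials per setting:

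| Active | Fence | Benchmark | Exclusion | Cap at this fence | Cap at a fixed 30 |
|---|---|---|---|---|---|
| 20% | 0 | −0.50 | 0 | 0 | −0.45 |
| 30% | 4.3 | −0.73 | +0.06 | −0.08 | −0.65 |
| 40% | 11.5 | −0.95 | −0.04 | −0.42 | −0.85 |
| 50% | 16.4 | −1.18 | −0.25 | −0.74 | −1.05 |

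At 20% active, exclusion removes about 320 of 1,600 students. At 40% it removes 8.8% of controls and 4.9% of PGC students, and the rejection rate at two-sided 0.05 is 92% for the benchmark, 7% for exclusion, 65% for the cap at this fence and 89% for the cap at 30. The value 30 is illustrative only.

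If PGC instead multiplies the share active by 0.75, exclusion loses less: −0.80 becomes −0.32 at 40% active, and −0.99 becomes −0.63 at 50%.

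**3. Fence among students not skipped out of the item**

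Under the skip patterns in 4c.iv the fence may in practice rest on this group. It is then positive; exclusion kept 5–65% of the effect and capping 41–91%.

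**The case against.** The strongest reply is that this is one of six sensitivity analyses, that comparing results with and without outliers is common, and that no primary estimate, p-value or Benjamini-Hochberg decision depends on it. All of that stands and limits the weight of the point.

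A reader might infer that the plan breaks its own intention-to-treat principle. It does not: that statement describes the main analysis, which keeps every flagged value, and sensitivity runs depart from the main analysis by design. Item 5 also drops students on post-randomisation behaviour.

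A reader might infer that the plan will declare the benchmark unreliable if the estimate falls. It says only that substantive differences will be reported. In item 6, by contrast, a discrepancy changes which model is reported. The risk lies in how an undefined difference will be read.

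Capping also attenuates a true effect, so a fall under capping is not proof of bad data either; the advantage is one of degree. Nor does a smaller estimate always mean lost significance. With the share-active effect at 40% active, rejection rose from 70% in the benchmark to 81% under exclusion, because the variance fell as well.

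Finally, capping at an all-student fence would repair nothing at 20% active and little at 30%. That objection is correct, and it decides how the remedy must be worded.

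**Conclusion.** The point holds as a limited one. Exclusion selects on the outcome and shrinks a real reduction: by 24–78% in the assumed frequency scenarios with a fence among non-zero reports, and almost wholly with an all-student fence at 20–40% active. The loss is smaller if PGC acts mainly on the share active and the fence is above zero. Capping at a sensible value loses 6–37% in the same frequency scenarios and still removes most of the influence of false values.

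The documents do not support a claim of bias in the main analysis or of false positives: the benchmark is untouched and there is no bias under the null. Nor would capping keep every randomised student, since those without usable 10th-grade data are deleted in any case; it keeps every student in the benchmark analytic sample. That exclusion drops the whole student is inferred from the missing-outcome rule; item 4 speaks only of data.

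The sizes rest on assumed active shares, tail shapes, effects and false values, and on a single total count, whereas the plan flags items.

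**What to change.** In 4c.iii, 4f.iv item 4 and Table 3, add a run in which values above a pre-specified cap are set to that cap, every student in the benchmark analytic sample stays in, and the same model is re-run. Define the cap with arms pooled, either as Q3 + 3 × IQR among non-zero reports or as a plausible maximum fixed before the data are seen. Say whether it applies to each item or to the summed outcome, and whether baseline values are treated in the same way.

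Show the exclusion run beside the capped run, with the number excluded per arm. State that a fall under exclusion alone will not be taken as evidence that the benchmark is not robust.

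The cost is a few sentences and one recode line. The drawbacks are some attenuation of a true effect and a little remaining influence from a false value (−0.16 against +0.02 in the example).

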Appendix A: Tables

Table 1. Behavioral outcomes used for primary impact analyses research questions

Outcome name	Description of the outcome, including how it is operationalized	Source of the measure	Timing of measure
Sexual initiation	
The risk outcome is operationalized as a dichotomous variable indicating whether a person reports having ever had sex or not having ever had sex.
 
The measure is calculated from the following item:
 
 • Have you ever had any type of sex (oral, vaginal, or anal)? 
A person who selects either Yes is given a value of 1 for the measure. A person who selects No is given a value of 0 for the measure.
 
The resulting variable is dichotomous with values 0 or 1, where 0 indicates a person who has never had any type of sex and 1 indicates a person who has had sex.
 
Note: The analytic sample will include all respondents who have tenth grade follow-up data.
	Participant Questionnaire	Beginning of tenth grade
Times having sex	
The risk outcome is operationalized as the number of times in the past three months a person reports having any type of sex.
 
The measure is calculated from the following items:
 
 • In the past 3 months, how many times have you had vaginal sex? • In the past 3 months, how many times have you had oral sex? • In the past 3 months, how many times have you had anal sex? 
The measure is calculated by summing the total number of times a person reported having vaginal, oral and anal sex.
 
The resulting variable is continuous with values that range from 0 to k, where 0 indicates that a person has not engaged in sex in the past three months, and k indicates the number of times the person has engaged in sex (risk behavior) in the past three months.
 
Note: The analytic sample will include all respondents who have tenth grade follow-up data. Persons who indicate they have not had sex will
	Participant Questionnaire	Beginning of tenth grade

be considered to have participated in the risk behavior 0 times (i.e., they did not engage in sex).			
Number of sexual partners	The risk outcome is operationalized as the number of sexual partners in the past three months.	Participant Questionnaire	Beginning of tenth grade
	
The measure is calculated from the following item:
 
 • How many sexual partners have you had in the past 3 months? 
The measure is calculated by summing the total number of sexual partners reported by the participant.
 
The resulting variable is continuous with values that range from 0 to k, where 0 indicates that a person has had no sexual partners in the past three months, and k indicates the number of sexual partners in the past three months.
 
Note: The analytic sample will include all respondents who have tenth grade follow-up data. Persons who indicate they have had no sexual contact will be considered to have 0 sexual partners.
		

Table 2. Covariates included in primary impact analyses

Covariate	Description of the covariate and how it will be used as a covariate in the analysis	Rationale for inclusion
Behavioral outcomes at baseline		
Sexual initiation	
The risk outcome is operationalized as a dichotomous variable indicating whether a person reports having ever had sex or not having ever had sex.
 
The measure is calculated from the following item:
 
 • Have you ever had any type of sex (oral, vaginal, or anal)? 
A person who selects either Yes is given a value of 1 for the measure. A person who selects No is given a value of 0 for the measure.
 
The resulting variable is dichotomous with values 0 or 1, where 0 indicates a person who has never had any type of sex and 1 indicates a person who has had sex.
	Sexual initiation is included in the primary impact analysis as the pre-intervention or baseline measure of the behavioral outcome; it is included in the models so that individual-level change or difference can be assessed at the 10 th grade follow-up.
Times having sex	
The risk outcome is operationalized as the number of times in the past three months a person reports having any type of sex.
 
The measure is calculated from the following items:
 
 • In the past 3 months, how many times have you had vaginal sex? • In the past 3 months, how many times have you had oral sex? • In the past 3 months, how many times have you had anal sex? 
The measure is calculated by summing the total number of times a person reported having vaginal, oral and anal sex in the past three months.
 
The resulting variable is continuous with values that range from 0 to k, where 0 indicates that a person has not engaged in sex in the past three months, and k indicates the number of times the person has engaged in sex in the past three months.
	Times having sex is included in the primary impact analysis as the pre-intervention or baseline measure of the behavioral outcome; it is included in the models so that individual-level change or difference can be assessed at the 10 th grade follow-up.
Number of sexual partners	
The risk outcome is operationalized as the number of sexual partners in the past three months.
 
The measure is calculated from the following item:
 
 • How many sexual partners have you had in the past 3 months? 	Number of sexual partners is included in the primary impact analysis as the pre-intervention or baseline measure of the behavioral outcome; it is included in the models so that individual-level change or difference can be assessed at the 10 th grade follow-up.

Covariate	Description of the covariate and how it will be used as a covariate in the analysis	Rationale for inclusion
	
The measure is calculated by summing the total number of sexual partners reported by the participant.
 
The resulting variable is continuous with values that range from 0 to k, where 0 indicates that a person has had no sexual partners in the past three months, and k indicates the number of sexual partners in the past three months.
	
Individual level covariates		
Age	
The variable is measured as the respondent's age in years at baseline.
 
The measure is constructed from the following item on the Participant Questionnaire:
 
 • Date of birth 
The variable is calculated by subtracting the reported date of birth from the date when the baseline questionnaire was completed.
 
The resulting variable is continuous.
	
Research has shown that likelihood of engaging in sex increases with age, while number of sexual partners increases (Brewster 1999; Kirby 2007; Miller et al 1998; Scott-Jones and White 1990)

Gender	
The measure is operationalized a set of $n-1$ dummy variables, where n refers to the categorized gender.
 
The measure is taken from the following item on the baseline Participant Questionnaire:
 
 • Which of the following best describes you? 
 ○ Female ○ Male ○ Transgender ○ Unknown ○ Other 
Responses are recoded into the following categories and dummy variables are created for each: Female, Male, Other (which includes individuals who report
	
Research has shown that males report a greater number of sexual partners and earlier sexual initiation (Miller et al 1998; Santelli et al 2000).

Covariate	Description of the covariate and how it will be used as a covariate in the analysis	Rationale for inclusion
Race	
Transgender, Unknown, or Other). Each dummy will be coded as 1 if the individual is coded as that particular gender and 0 otherwise.
 
The measure is operationalized a set of $n-1$ dummy variables, where n refers to the categorized race.
 
The measure is taken from the following item on the baseline Participant Questionnaire:
 
 • What is your race? (Participants can select more than one response) 
 ○ White ○ Black or African American ○ Hispanic, Latino, or of Spanish origin ○ American Indian or Alaska Native ○ Asian ○ Native Hawaiian or Pacific Islander ○ Some other race (specify) 
The category Hispanic, Latino, or of Spanish Origin is not considered in the operationalization of the race variable (it is used to create a separate Hispanic/Latino indicator variable). Remaining responses are recoded into the following mutually exclusive categories and dummy variables are created for each: White only, Black only, Other race only (which includes American Indian/Alaskan Native, Asian, Native Hawaiian/Other Pacific Islander, and Other), Race not selected (individual did not select any racial category), and Multiracial (which includes individuals who selected more than one racial category).
 
Each dummy will be coded as 1 if the individual is coded as that particular race and 0 otherwise.
	
Research has shown that Black/African American and Hispanic adolescents are more likely to engage in sex during adolescence and initiate sexual activity at a younger age (Blum 2000; Brewster 1999; Hogan et al 2000; Kirby 2007; Scott Jones and White 1990)

Hispanic, Latino or of Spanish origin	
The measure is operationalized as a dummy variable, where 0 = identify as another ethnicity/do not identify ethnicity; 1 = identify as Hispanic, Latino or of Spanish origin.
 
The measure is taken from the following item on the baseline Participant Questionnaire:
	
Research has shown that Black/African American and Hispanic adolescents are more likely to engage in sex during adolescence and initiate sexual activity at a younger age (Blum 2000; Brewster 1999; Hogan et al 2000; Kirby 2007; Scott Jones and White 1990)

Covariate	Description of the covariate and how it will be used as a covariate in the analysis	Rationale for inclusion
	
 • What is your race? (Participants can select more than one response) 
 ○ White ○ Black or African American ○ Hispanic, Latino, or of Spanish origin ○ American Indian or Alaska Native ○ Asian ○ Native Hawaiian or Pacific Islander ○ Some other race (specify) 
Variable will be coded as 1 if participant self-identified as Hispanic, Latino or of Spanish origin, regardless as to whether other races/ethnicities are specified; Hispanic, Latino or of Spanish origin is not selected, the response will be coded as 0.
	
Blocking Covariates		
School	
The measure is operationalized a set of $n-1$ dummy variables, where n refers to the number of participating schools over the course of the evaluation period.
 
Data for the measure are obtained from the Randomization dataset.
 
Each dummy will be coded as 1 if the individual is enrolled in a particular school and 0 otherwise. School 1 is the reference variable. Dummy variables will be grand mean centered so that the intercept will then reflect the un-weighted mean site effect.
	Randomization is blocked by school.

Table 3: Data Editing Rules

The following table provides PRG's general rules for editing data based upon responses given.

Category	Data editing rule
No response given to an item (coded as .f)	If data from a related variable can be used to infer a value, data will be logically edited. Otherwise, the value will be left as missing.
Invalid items (coded as .i)	Adjust missing baseline values
Outlying items (Outlier indicator variable coded as 1)	Keep in benchmark analysis; run sensitivity analyses excluding outliers
Inconsistent across-time items (coded as .k)	Adjust missing baseline values
Unreliable cases (Unreliable indicator variable codes as 1)	Exclude case from benchmark analysis; run sensitivity analyses including unreliable cases

**EVALUATION ABSTRACT:
THE EVALUATION OF PEER GROUP CONNECTION IN RURAL
NORTH CAROLINA AND NEW YORK CITY, NEW YORK**

Grantee

Grantee Name: Center for Supportive Schools
Project Lead: [name], Psy.D.
Email address: [contact]

Evaluator

Evaluator's Organization: The Policy & Research Group
Evaluator Lead: [name].
Email address: [contact]

Intervention Name

Peer Group Connection

Intervention Description

Peer Group Connection (PGC) is a school-based, cross-age, group peer mentoring program for 9th-grade students designed to facilitate the transition into high school and improve non-cognitive abilities (for example, grit, decision making skills, goal-setting skills), student engagement, and educational outcomes. The program leverages existing resources, such as school staff, parents, and student leaders, to create a supportive environment for new high school students that encourages them to attend school, set personal goals, work hard, and make healthy decisions. By offering additional support to 9th-grade students, the program seeks to mitigate problems often associated with the transition into high school, such as disengagement from school, absenteeism, declines in academic performance, and engagement in risk behaviors. Although PGC is not explicitly a sexual health or teen pregnancy prevention program, the belief is that by engaging 9th-grade students in school, building connectedness among peers, and building students' decision making and goal-setting skills, PGC will encourage students to make healthier decisions, including reducing sexual risk-taking and increasing protective behaviors.

PGC requires the integration of several key groups that work together to ensure the peer mentoring program is implemented as intended: (1) a stakeholder team consisting of faculty members, parents, and students who work together to make programmatic decisions and incorporate the program into the school; (2) faculty advisors, selected by the stakeholder team, who are trained to run the program and teach a daily leadership course to peer leaders; and (3) 11th- and 12th-grade peer leaders who are trained in a daily leadership development class and facilitate the 9th-grade peer mentoring program.

Although the peer mentoring component of PGC is adjustable to meet the particular requirements of a school, typically the program begins with a full-day retreat during which faculty advisors and peer leaders introduce 9th-grade participants to PGC goals and expectations. Then around the third week of the school year, 9th-grade participants begin attending weekly peer group outreach sessions led by older peer leaders. Outreach sessions occur during regularly scheduled classes (participants are pulled from their classes to attend); they include hands-on activities, simulations, and discussions intended to build group cohesion and improve the decision making skills of group members. Topics include the importance of showing up to class, sharing cultures and backgrounds, learning effective communication skills, and how to set and effectively reach goals. PGC can occur in either a half-year (semester) or full-year format. In either format, a minimum of 18 45-minute outreach sessions are expected to be offered to PGC participants during the course of their 9th-grade year.

Comparison Condition

Business as usual

Comparison Condition Description

The comparison condition is "business as usual," consisting of normally scheduled classes or activities (for example, Physical Education/Health class, elective class, or homeroom period) assigned to comparison group participants during the period the PGC outreach pullout occurs. Comparison group participants will therefore receive more time in the regularly scheduled class than the treatment group, but there will be no alternative program or additional activities offered to the participants assigned to the comparison group. Although normally scheduled classes or activities might include sexual or reproductive health information, school administrators have confirmed that PGC outreach will occur in classes and on days only when no sexual or reproductive health components are taught. Therefore, exposure to sexual health content should be equal between treatment and comparison group participants.

Behavioral Outcomes

Sexual initiation, frequency of sexual intercourse, and number of sexual partners

Non-behavioral Outcomes

Connectedness among peers; competence in peer relationships; school engagement and attachment; self-efficacy in peer interactions; self-efficacy in goal setting and decision making skills; growth mindset; grit; educational aspirations; educational outcomes (for example, drop out, suspension, on-time grade promotion); intentions to practice safe sex (that is, use contraceptives, refuse unprotected sex, limit number of sexual partners); subjective norms concerning sex

Sample and Setting

High schools participating in the study serve large populations of economically disadvantaged and minority students in communities with high teenage birth rates. In North Carolina, partner schools are located in rural areas, some with substantial Hispanic populations, and in New York City, partner schools are located in urban areas and serve largely Hispanic, African American, and other minority populations.

Four basic eligibility criteria have been established for participation in the study. To be eligible for enrollment into the study, students must: (1) be enrolled at a study school; (2) provide parental consent and personal assent to participate in the study; (3) meet basic requirements for data collection (students must have the ability to complete a self-administered Participant Questionnaire, which is available in English and Spanish, in a classroom or group setting, unassisted, in 60 minutes or less.); and (4) be entering the 9th grade for the first time. Staff will screen all incoming 9th graders enrolled in a study school for eligibility. The sample will include eligible youth enrolled in the study; in all, the expectation is that approximately 1,600 9th graders will enroll in the study over the implementation period.

Research Design and Data Collection

The study is an individual randomized controlled trial in which eligible, consenting 9th-grade participants who volunteer to be pulled out of their regularly scheduled classes are randomly assigned by the evaluator to intervention (PGC) or control (business as usual) groups at a one-to-one ratio. The unit of assignment is the individual, and random assignment occurs after obtaining evaluation consent and assent and before the provision of any programming or collection of baseline data. Study participants are not informed that they are in the treatment or comparison group before baseline data collection. However, it is likely that some students will be aware of their PGC participation status before baseline data collection. In many schools, students will receive their schedules before baseline, and the schedules will include notation that a class is a PGC pullout class.

Youth in the intervention and comparison groups will receive a baseline survey and youth enrolled in the 2016-17 school year will receive a 12-month follow-up survey. Baseline data collection occurs during the fall of their 9th-grade year (before the provision of any PGC programming); follow-up data collection occurs during the fall of the 10th-grade year and will only be completed for study participants enrolled during the 2016-17 school year due to the shortened project period ending June 2018. In-school data collection is the preferred method of data collection for all data collection time points. If students no longer attend the study school or miss all available make-up administrations, they are offered the questionnaire first through an online administration, and then through mail. If students no longer attending the school do not complete an online or mail questionnaire, evaluation staff will attempt to conduct a phone interview using an abbreviated version of the questionnaire. Data collection procedures are the same for treatment and comparison groups.

For the implementation evaluation, PGC program staff will collect data on fidelity and adaptations, attendance, and quality. Staff will collect these data through observation forms, questionnaires, and attendance logs. PGC program staff (Center for Supportive Schools) complete the observations forms, school staff and students complete questionnaires, and attendance records are obtained from the school and maintained by PGC program staff.

Schedule/Timeline

